Previous observational studies have reported an association between higher air pollution exposure and lower attention in children. With this project, the investigators aim to confirm this association in adolescents using an experimental design. In addition, the study will assess the relationship between air pollution exposure and individual decision-making with respect to risk, time and social considerations. High school students in 3rd grade (ESO, 14-15 years of age) in different high schools in the Barcelona province (Spain) will be invited to participate. For each class in each high school, participating students will be randomly split into two equal-sized groups. Each group will be assigned to a different classroom where each participant will complete several activities during two hours, including an attention test (Flanker task) and a reduced version of the Global Preferences Survey. One of the classrooms will have an air purifier that will clean the air. The other classroom will have the same device but without the filters, so it will only re-circulate the air without cleaning it. Students will be masked to intervention allocation. The investigators hypothesize that students assigned to the clean air classroom will have better scores in the attention test, and that decision-making will also present differences between the two classrooms.

Objectives

The objectives of the study are to identify if cleaning the air of a classroom has an impact on:

- 1) The attention of high-school students
- 2) The individual preferences with respect to risk, time and social considerations

Study Methods

Trial Design and Randomization

This is an interventional, randomized, 2-arm trial with equal allocation. Allocation will be done completely at random. Briefly, for each class in each high school, participating students will be randomly split into two equal-sized groups, and each group will go to a different classroom to perform the same activity for two hours. The two classrooms need to be as similar as possible in terms of size, orientation and windows. The two classrooms will have an identical air purifier (Pure Airbox, Zonair 3D) that will be running from 30 minutes before the session until the end of the 2-hour session. The purifier in one room will have the filters installed, and therefore will clean the air, while the purifier in the other classroom will not have the filters installed (sham device that will simply recirculate the air without filtering it). Participants will be masked to the intervention. Assignment of purifier to classroom will be done at random.

During the whole time, we will have measure continuously in both classrooms the concentrations of black carbon with Microaeth (AethLabs, USA), the concentration of PM_{2.5} with DustTrak (TSI, USA), the levels of CO₂ and values of temperature and humidity (Extech, USA).

Once students are in the classroom they have been assigned to, they will complete several activities, including several validated tests and tasks. All of them will be administered though a

laptop (each student will be provided one laptop with the tests and questionnaires). The tests and questionnaires will be completed using headphones to block the noise.

The chronology of the activities will be the following:

- Assignment of groups to classrooms, initial explanation (10 minutes).
- Completing the baseline Attention Network Task (ANT, adult version, Flanker task) (15 minutes).
- Completing the PMA-R (Primary Mental Aptitudes) test (10 minutes).
- Watch several videos related to Science and Environment (50 minutes).
- Completing a questionnaire about the videos (5 minutes).
- Completing the post Attention Network Task (10 minutes).
- Completing a questionnaire on factors that can affect attention, designed by the students (10 minutes).
- Completing a short version of the Global Preferences Survey (10 minutes).

Sample size Calculation

A previous study (Sunyer et al., 2017) detected a mean reduction of 5 ms in the hit reaction time standard error for correct answers (HRT-SE) calculated from the ANT test, which we will take as our main outcome, associated with a 37% increase in the concentration of NO₂, a marker of exposure to traffic pollution. With the air purifier it is expected to achieve a 80% reduction in the concentration of fine particles, which is why we expect to find a difference of 10 ms in HRT-SE between the group that goes to the purified classroom and the ones that go to the regular classroom. Bearing in mind that the standard deviation of HRT-SE is 90 ms (Sunyer et al., 2017), to have a statistical power of 80% with a type I error of 5% in the comparison of the two groups, it is necessary to include 2,500 students. Assuming a participation of 25 of the 30 children for each participating class, the participation of 100 classes is required. By recruiting high schools with 2 or more lines, it is expected to have to recruit about 35 high schools.

Statistical analyses will be conducted after all information for all participants has been collected.

Statistical Principles

Statistical significance will be considered at the 5% level. Results will be provided with 95% confidence intervals.

Adherence to protocol will be defined as staying in the classroom during the 2 hours, or in exceptional cases, leaving it for less than 5 minutes. Adherence will be described as percentage of students being adherent. Non-adherent students will be excluded from statistical analyses.

Trial Population

Eligibility criteria: all students in the 3rd grade of ESO in participating high schools and with informed consent signed by them and by the parents will be eligible for the analysis. There are no exclusion criteria.

The CONSORT flow diagram will include the number eligible, the number that did not participate, the number allocated in each arm, the number not adherent (with reasons), and the excluded from the analyses (with reasons). Anticipated reasons for exclusion from analyses

include: missing data in an outcome (the subject will be excluded from the analyses of that outcome) or low accuracy tests. For ANT, a test will be considered of low accuracy if the number of correct responses is less than 70%. Reaction times (RT) below 100 ms will be excluded from RT calculations because of physiological implausibility implying that such a response is perseverative or anticipatory, although this does not imply the exclusion of the subject (other RT are available).

Baseline characteristics will be summarized by providing, for each arm, percentages for categorical variables and medians and 1st and 3rd quartiles for continuous variables. The following baseline variables will be summarized: sex, age, PMA-R results, and baseline ANT measures.

Analysis

Analysis on Attention

Outcomes

Attention outcomes are all derived from the Attention Network Task-Flanker Task (ANT). It is a computerized test that takes approximately 9 minutes to complete. A row of five arrows appears either above or below a fixation point. Participants have to use the arrow keys from the keyboard to indicate as quickly as possible if the central arrow is pointing to the left or to the right. They have to ignore the flanker arrows, which point in either the same (congruent) or opposite (incongruent) direction than the middle arrow. The target can be preceded by no cue; a center cue or a double cue, which inform about the upcoming of the target but not on its location; or an orienting cue that alerts about the upcoming of the target as well as its location (orienting cue). The task is divided into four experimental blocks of 32 trials each (a total of 128 trials).

The primary outcome regarding attention will be the response speed consistency throughout the post Attention Network Task-Flanker Task (ANT). It will be calculated as hit reaction time standard error (in milliseconds) for correct responses (HRT-SE). A higher HRT-SE indicates highly variable reactions related to inattentiveness.

Secondary outcomes include the following, derived from the post ANT:

- Impulsivity, calculated as the number of incorrect responses (responses made in the opposite direction to the direction of the target arrow).
- Selective attention, calculated as the number of omission errors (failure to respond to the stimulus).
- Alerting score, computed subtracting the median reaction time (RT) in milliseconds for double cue from median RT for the no cue condition (calculations performed after removing the incongruent trials).
- Orienting score, computed subtracting the median RT in milliseconds for spatial cue from the RT for central cue (calculations performed after removing the incongruent trials).
- Conflict score (executive attention), calculated as the median RT in milliseconds for each flanker condition (across cue conditions) and subtracting the congruent from the incongruent RTs.

Analysis Methods

Analyses will be conducted using conditional linear regression using class (the group of 30 students from the same class in the same high school that were randomly split into each arm and that undertook the experiment on the same day and time) as strata. This way, the analysis will be automatically matched by high school, class, day and time of the day. Intervention arm will be the explanatory variable of interest in the model. The coefficient associated with arm will then be interpreted as the mean difference in the outcome when comparing the two arms. Models will be adjusted for year of birth; sex; average temperature during the experimental session; average relative humidity during the experimental session; and average CO₂ concentration during the experimental session; as these conditions can differ in the two classrooms.

Analysis of residuals will be used to detect influential observations using DFBeta. Analyses will be repeated by excluding subjects with DFBetas clearly separated from the rest.

Sensitivity analyses will include:

- Additionally adjusting the models for the same outcome measured in the baseline session.
- Additionally adjusting the models for the results of the PMA-R test (number of correct responses).
- Replacing the arm indicator by the average values of black carbon from the beginning of the experiment to the end of the post ANT test. In this case, the effect of black carbon on the outcome will be reported by an interquartile range increase. This analysis will allow taking into account the difference in black carbon levels in the two classrooms, i.e. it will not estimate a common change in the outcome for all strata. Linearity of the association will be examined using generalized additive models (GAM). If visual inspection of the resulting exposure-response relationship suggests a non-linear association, we will try to transform variables to achieve linearity. If transforming variables does not work, we will report the curve estimated by the GAM models.
- Same as the previous point, but using PM_{2.5} levels instead of black carbon.

Subgroup analyses will be conducted by sex using the same methodology described above.

Missing Data

Missing data are only expected in the outcome variables if the participant did not complete the test, in which case it will be excluded. Other potential cases of missing data include an error in the monitors that precludes proper adjustment for covariates. If there are missing values for CO₂, temperature or humidity in one of the classrooms, we will replace them by the values from the other classroom, provided that this approach is reasonable according to the data obtained in the other classrooms. Otherwise, the classroom will be excluded from the adjusted analyses, but an unadjusted analysis including all classrooms will also be carried out to compare the results. For the analyses using black carbon or PM_{2.5} concentrations, missing values on these two variables will be imputed using the baseline value in the other classroom and the rate of reduction over time estimated in all other classrooms with sham or real air purifier, as appropriate.

Statistical Software

Analyses will be conducted in the Stata and R softwares. Stata command `xtreg` with the fixed effects option will be used to fit conditional linear regression models, which can also be fitted using regular linear regression commands in Stata (`regress`) or R (`lm`) by including a strata factor as adjustment variable. GAM models will be fitted using the `mgcv` package in the R software. The `tlm` package in R will be used to interpret models with transformed variables (Barrera-Gómez and Basagaña 2015).

Analysis on Decision-making with respect to Risk, Time and Social Considerations

Outcomes

The primary outcomes of analysis will be the (1) risk taking scores, (2) time preference scores, (3) the positive reciprocity scores, (4) the altruism scores, and (5) the self-assessment of trust. All the scores will be measured from the responses to the questionnaire, which is a subset of the questionnaire in Spanish used in Falk et al (2018). For each of the traits (risk preferences, time preferences, positive reciprocity, altruism, and trust), an individual-level index will be computed that aggregates responses across different survey items following the methodology in Falk et al. (2018).

Analysis Methods

The analysis will follow the basic analysis of Falk et al (2018), where groups, instead of being countries, will be our arms. In addition, we will follow the empirical strategy described above for the analysis on attention. That is, we will perform regression analysis, controlling for the relevant observable variables such as gender, age, cognitive ability, attention outcomes, and other physical variables measured at the time of the experiments such as temperature, relative humidity, or average CO₂ concentrations. We will also control for outliers, and will study heterogeneous treatment effects.

Missing Data

In terms of missing values in the questionnaire on preferences, we will follow the methodology of Falk et al (2018, Section I.H): “If one (or more) survey items for a given preference were missing, then the missing items will be predicted using the responses to the available items:

- Suppose the preference was measured using two items, call them *a* and *b*. For those observations with missing information on *a*, the procedure will be to predict its value based on the answer to *b* and its relationship to *a*, which was estimated by regressing *b* on *a* for the subsample of subjects who had nonmissing information on both, *a* and *b* (on the world sample).
- For the unfolding-brackets time and risk items, the imputation procedure will be similar, but making additional use of the informational content of the responses of participants who started but did not finish the sequence of the five questions. Again suppose that the preference is measured using two items and suppose that *a* (the staircase measure) is missing. If the respondent did not even start the staircase procedure, then imputation will be done

using the methodology described above. On the other hand, if the respondent answered between one and four of the staircase questions, a will be predicted using a different procedure. Suppose the respondent answered four items such that his final staircase outcome would have to be either x or y. A probit was run of the “x vs. y” decision on b, and the corresponding coefficients were used to predict the decision for all missing values (note that this constitutes a predicted probability). The expected staircase outcome will be then obtained by applying the predicted probabilities to the respective staircase endpoints, i.e., in this case x and y. If the respondent answered three (or less) questions, the same procedure was applied, the only difference being that in this case the obtained predicted probabilities were applied to the expected values of the staircase outcome conditional on reaching the respective node. Put differently, the procedure outlined above was applied recursively by working backwards through the “tree” logic of the staircase procedure, resulting in an expected value for the outcome node.

– If all survey items for a given preference were missing, then no imputation will take place”

Statistical Software

Analyses will be conducted in Stata and Matlab.

References

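### Students are excluded after randomisation and no all-randomised analysis is planned; if the 70% accuracy rule covers the post ANT, it may attenuate the two error-count outcomes

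*SAP*

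**What the plan says.** The SAP, under Statistical Principles, defines adherence as staying in the room for the full two hours, with an exceptional allowance for "leaving it for less than 5 minutes". It then states: "Non-adherent students will be excluded from statistical analyses". No limit is set by outcome or by when the absence occurred.

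Under Trial Population, the anticipated reasons for exclusion are "missing data in an outcome (the subject will be excluded from the analyses of that outcome) or low accuracy tests", followed by "For ANT, a test will be considered of low accuracy if the number of correct responses is less than 70" percent. The next sentence says that discarding implausibly fast reaction times does not remove the student. By contrast, this suggests that a low-accuracy test does.

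Under Analysis on Attention: "Secondary outcomes include the following, derived from the post ANT". The list begins "Impulsivity, calculated as the number of incorrect responses" and continues with selective attention, the count of omissions. The task has 128 trials. Analysis Methods reads the arm coefficient as the mean difference in outcome between arms, and Statistical Principles adds: "Results will be provided with 95% confidence intervals". The CONSORT diagram is to show "the number not adherent (with reasons), and the excluded from the analyses (with reasons".

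**The concern.** Both exclusions are decided after allocation and during exposure. Even the baseline ANT is taken in the assigned room with the purifier already running. Selection at that stage can undo the balance that randomisation gives, and without an all-randomised analysis a reader cannot see what either rule changed.

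The 70% rule raises a further issue. As a validity check on reaction times it is reasonable. Applied to error counts, it uses the outcome to decide who is analysed for that outcome. If unfiltered air worsens accuracy, more sham than clean-air students would fail it, and the difference among those who remain would be smaller than the difference among all students.

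The scope of the rule is also open. The SAP does not say whether it means the baseline ANT, the post ANT or both. It limits exclusion for missing data to the outcome concerned, but gives no such limit for low-accuracy tests. The decision-making models adjust for attention outcomes, so a dropped ANT might drop a student there too. Two analysts could build different datasets from this text.

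**Working it through.** **Is anyone restored?** The SAP's sensitivity analyses add baseline-outcome or PMA-R adjustment, or replace arm by black carbon or PM2.5. The DFBeta rerun removes further students. The unadjusted comparison of all classrooms deals only with missing CO₂, temperature or humidity. The protocol defers data analysis to the SAP. So no planned analysis restores the excluded students.

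**Timetable.** 10+15+10+50+5+10 = 100, so the post ANT ends at minute 100 of 120. A student who leaves after that for 5 minutes or more loses an attention result already recorded.

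**Cap.** 0.70 × 128 = 89.6, so at least 90 correct responses are needed. Incorrect plus omitted responses are then at most 128 − 90 = 38. The cap is on the sum.

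**The plan's sample size.** With 10 ms, SD 90 ms, two-sided 5% (assumed) and 80% power: n per arm = 2 × (1.96 + 0.84)² × 90²/10² ≈ 1,272, or 2,544 in total. The stated 2,500 is 1.7% lower. At 1,250 per arm the SE is 90 × √(2/1,250) = 3.60 ms, and power is Φ(10/3.60 − 1.96) = 79.3%.

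**Adherence rule.** If 2% are excluded equally (assumed), N = 2,450 and power is 78.5%.

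**Error counts.** All error rates here are assumed. The model is a beta-binomial on 128 trials, keeping totals of 38 or less, with 1,250 independent students per arm and a normal approximation. Clean-air mean error is 3, 5, 8, 10 or 15%; within-student ICC is 0.02, 0.05, 0.10 or 0.20; sham errors are 1.10 or 1.22 times higher. That makes 40 cells, of which 28 have at most 5% of sham excluded. With D the full difference and D′ and SE′ the retained difference and its SE, the loss is 1 − D′/D. Coverage is P(|Z + b| < 1.96), where b = (D − D′)/SE′ and Z is standard normal.

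| Mean error, ICC, ratio | D | D′ | Sham SD, full / cut | Power, full / cut | Coverage | Excluded, clean / sham |
|---|---|---|---|---|---|---|
| 5%, 0.10, 1.22 | 1.41 | 1.19 | 10.0 / 8.3 | 95.7 / 95.9% | 90% | 1.4 / 2.0% |
| 5%, 0.20, 1.22 | 1.41 | 0.89 | 13.9 / 8.5 | 75.4 / 76.3% | 66% | 3.9 / 4.9% |
| 8%, 0.10, 1.10 | 1.02 | 0.80 | 11.9 / 9.3 | 59.7 / 57.2% | 91% | 3.2 / 3.9% |
| 15%, 0.02, 1.22 | 4.22 | 3.62 | 8.2 / 7.2 | 100 / 100% | 46% | 1.4 / 4.5% |

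Results over the 28 cells:
- The loss is 0-36%, median about 10%; 12 cells lose under 5%.
- Coverage is 46-95%, median about 94%, and below 90% in 8 cells.
- Power changes by −2.5 to +4.0 points, because the cut also removes the high counts that inflate the SD.
- In the 18 cells with at most 2% of sham excluded, the loss is 0-15% and coverage about 90-95%.

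A different model (gamma-Poisson, 10% fewer errors in clean air) agrees in direction. With sham means of 8 incorrect and 4 omitted and gamma shape 1, 4.4% of sham and 3.2% of clean are excluded. The incorrect-response difference shrinks from 0.80 to 0.45, a loss of about 44%. With no true effect the difference stays at about 0. Over its whole range the loss runs from under 1% to about 83%, the latter with 14.5% of sham excluded. The 36% is therefore the edge of one grid, not a bound.

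**HRT-SE.** With HRT-SE and inaccuracy bivariate normal (correlation ρ), sham cut at t and the clean-air arm shifted by 10/90 = 0.11 SD, the retained difference is 10 − 90ρ[λ(t) − λ(t + 0.11)], where λ = φ/Φ. The results are:
- 1% of sham excluded, ρ 0.3: 9.83 ms, power 77.8%.
- 3%, ρ 0.5: 9.37 ms, 74.2%.
- 5%, ρ 0.7: 8.76 ms, 70.2%.
- No shift in accuracy: 10.0 ms, 78.0-81.1%.
- If 10 ms and 90 ms already describe retained students, only n falls: 79.0, 78.2 and 77.5% at 1, 3 and 5% excluded.

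**The case against.** Any bias in the error counts needs three conditions: the rule covers the post ANT, air changes accuracy, and enough students fall below 70%. The documents establish none of them. The post ANT is the natural reading, since the outcomes come from it, but it is not stated. It would therefore go too far to infer that the plan biases the two secondary outcomes outright, or that it manufactures a benefit.

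The sizes rest on assumed inputs, and the extremes are not typical. The 46% coverage cell supposes a difference of about 0.5 SD (4.22 on an SD near 8), almost five times the planned 0.11 SD, and power there is 100% either way. The 66% cell is about 0.10 SD (1.41/13.9), so material bias remains possible at a plausible effect.

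A test under 70% correct may reflect disengagement rather than impulsivity. The cut-off also reduces noise: on root mean squared error it is equal or better in 20 of the 28 cells. That stands, and it argues against simply replacing the cut-off version by the uncut one.

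The adherence rule is pre-specified, its counts and reasons will be reported, and masking makes unequal absence less likely. Finally, the SAP speaks of low-accuracy tests, so exclusion per test is a plausible reading and loss from the decision-making models is not shown. What these points leave standing is the missing all-randomised analysis and the unstated scope.

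**Conclusion.** The concern holds in a limited form and should be fixed. That students are removed after randomisation and that no planned analysis restores them follows directly from the text. The cap of 38 follows by arithmetic if the 70% rule covers the post ANT.

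Attenuation of the error-count differences is conditional. It is typically about 10% in the grid examined and can be much larger, but the true size cannot be known from the documents. Where it occurs, the cost is mainly an understated effect and an interval centred too near zero, rather than lost power.

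A reader might also infer that the primary HRT-SE comparison is compromised. The documents do not support that. Attenuation there needs air to shift accuracy and the planning values to describe data without the cut-off, and neither is established. The adherence rule mainly costs precision, 0.8 points of power at an assumed 2%, unless absences differ by arm.

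**What to change.** 1. Make the main analysis all randomised students with the outcome recorded, in the arm assigned, regardless of time out of the room. Keep exclusion of non-adherent students as a sensitivity analysis.
2. For impulsivity and selective attention, report results with and without the 70% cut-off. Do not describe the cut-off version as the mean difference for all students.
3. For HRT-SE and the other reaction-time scores, keep the cut-off as a test-validity rule and co-report all students with computable reaction times.
4. State which ANT the rule refers to, that it applies per test, and that it does not remove a student from the decision-making models. Split the planned exclusion counts by arm.

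The cost is SAP wording and one extra set of model runs, with no new data. The uncut error counts will be noisier: in the 28 cells their CI is up to about 59% wider (2.09 against 1.31 errors at mean error 5%, ICC 0.20, ratio 1.22). The planned DFBeta rerun already offers a check on extreme restored tests.

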Attention processes are an interesting option to study the effects of air pollution with experiments, as they can fluctuate within the same day and are susceptible to the effects of environmental variables. Attention processes are essential complex cognitive functions for learning that include alerting, or ability to have and maintain vigilance during a task; the orientation, which involves shifting the attention from one stimulus to another when required; and executive attention, which involves detecting and resolving conflicts between responses, detecting errors or inhibiting responses. Our previous observational study was the first to investigate the relationship between exposure to air pollution and changes in attention in the short-term (within 24 hours) (Sunyer et al., 2017). An experimental study in 10 adults detected changes in frontal cortex activity, related to attention processes, 30 minutes after starting exposure to air pollution (Crüts et al., 2008), which supports the hypothesis that the effects of air pollution can occur quickly.

There exists a very recent economic literature showing that the variability among individuals in their cognitive functions is an explanatory factor on the variability in their preferences with respect to time and risk (Dohmen et al 2010; Proto et al, forthcoming). Hence, there exists the potential that air pollution may also affect individual preferences on risk and time, as well as on social considerations, like reciprocity and trust. These three elements (time, risk and social considerations) are essential in the understanding of individuals' decision-making process, and hence lie at the core of the economic analysis. However, there are no controlled experiments that have studied the direct effect of air pollution on economic decision-making.

Hypotheses and objectives

The objective of the study is to evaluate the attention of students exposed to purified air (low pollution) and those exposed to the metropolitan area of Barcelona (high pollution) levels through an experiment Randomized with air purifiers, and compare the results. The hypothesis is that exposure to contamination worsens the attention of students.

The objectives of the study are to identify if cleaning the air of a classroom has an impact on:

- 1) The attention of high-school students
- 2) The individual preferences with respect to risk, time and social considerations

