The investigators hypothesize that students assigned to the clean air classroom will have better scores in the attention test, and that decision-making will also present differences in the two classrooms.

Study Design

Participants and recruitment

The subjects of study will be students of 3rd grade (ESO) of high schools of the metropolitan area of Barcelona that accept to participate in the study. The participating high schools will distribute informed consent forms so that both the students and their parents or legal guardians sign it as an agreement to participate in the study. Only students with the signed informed consent will participate.

Experiment

This is a randomized experiment that will link air pollution levels with attention processes and decision making of the participants. The experiment will randomly split each class of maximum 30 students into two groups. Each group will go to a different classroom (but equivalent in size, orientation and windows) to perform the same activities for a duration of two hours.

The two classrooms will have an air purifier (Pure Airbox, Zonair 3D, capable of filtering the entire air of a 45 m² room every 10 minutes). The air cleaner in one of the rooms will have the filters installed, and thus will clean the air, while the air cleaner in the other classroom will not have the filters installed, and therefore it will simply recirculate the air without filtering it. This will allow masking the experimental arm to the study participants.

Preparation of classrooms

Field workers will arrive 30 minutes before the experiment begins to prepare the classrooms. Air purifiers will be installed in classrooms, which will begin to work with empty classrooms. Air purifiers will be running from 30 minutes before the experiment until the end of the 2-hour experimental session. Laptop computers with the tests and questionnaires to be administered will be installed in the classroom (each student will have a laptop). We will install in each of the classrooms the following monitors that will run continuously from 30 minutes before the session until the end of the 2-hour experimental session: a Microaeth (AethLabs, USA) to measure black carbon levels; a DustTrak (TSI, USA) to measure particulate matter with a diameter of less than 2.5 µm (PM_{2.5}); and an Extech (USA) to measure levels of CO₂ and values of temperature and humidity.

Participation of students in the classrooms

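### The first ANT and the PMA-R are taken after differential exposure has begun, and the preference regressions control for post-exposure cognitive measures on the proposed causal route

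*SAP*

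**What the plan says.** Protocol and SAP agree on timing. Protocol, Preparation of classrooms: "Air purifiers will be running from 30 minutes before the experiment until the end of the 2-hour experimental session". SAP, Trial Design and Randomization: "running from 30 minutes before the session until the end of the 2-hour session". The SAP also places all testing after allocation to a room: "Once students are in the classroom they have been assigned to, they will complete several activities, including several validated tests and tasks". Both chronologies begin with assignment to rooms, followed by the first ANT and then the PMA-R. No attention or reasoning test is scheduled earlier.

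The SAP uses the two tests in three ways:

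- **Baseline table** (Trial Population): "The following baseline variables will be summarized: sex, age, PMA-R results, and baseline ANT measures".
- **Attention sensitivity models** (Analysis on Attention, Analysis Methods): "Additionally adjusting the models for the same outcome measured in the baseline session", and separately for the PMA-R score. The main attention model has arm, class strata, year of birth, sex, temperature, humidity and CO₂ only.
- **Preference regressions** (Analysis on Decision-making, Analysis Methods): "controlling for the relevant observable variables such as gender, age, cognitive ability, attention outcomes". No specific measure is named. The PMA-R is the only intelligence measure described in the protocol, and the SAP defines the attention outcomes from the post ANT.

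The protocol's Introduction gives variation in cognitive function as the reason why pollution might alter preferences. In support of fast effects it cites an experiment in 10 adults with frontal-cortex changes "30 minutes after starting exposure to air pollution".

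**The concern.** A baseline covariate is safe to adjust for because treatment cannot have affected it. Here that rests on an unstated assumption that filtration has no effect in the first 10 to 35 minutes. If it does have one, three things follow.

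1. In the preference models, controlling for the PMA-R and for post-ANT scores removes whatever part of the arm effect runs through cognition, which is the route the protocol puts forward. The remaining arm coefficient is no longer the simple randomized contrast. This concerns five of the protocol's six primary outcomes.
2. In the attention sensitivity models the arm coefficient is attenuated. A smaller estimate could be misread as showing that the primary result is not robust.
3. In the baseline table an arm difference could be chance or an early effect. The table cannot separate them, and its label presumes chance.

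**Working it through.** **1. The plan's own figure.** Inputs from the SAP sample size section: difference 10 ms, SD 90 ms, power 80%, type I error 5% (taken as two-sided), equal allocation. n per arm = 2 × (1.960 + 0.842)² × 90² / 10² = 1,272, total 2,544, against 2,500 stated. With 1,250 per arm, SE = 90 × √(2/1250) = 3.6 ms and power is 79.3%. The stated size is reproduced.

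**2. Timeline, by summing the listed durations.**

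| Activity | Session minute | Minutes since purifier on |
|---|---|---|
| Assignment, explanation | 0-10 | 30-40 |
| First ANT | 10-25 | 40-55 |
| PMA-R | 25-35 | 55-65 |
| Videos | 35-85 | 65-115 |
| Video questionnaire | 85-90 | 115-120 |
| Post ANT | 90-100 | 120-130 |
| Student questionnaire | 100-110 | 130-140 |
| Preferences survey | 110-120 | 140-150 |

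Students have had at most 10-25 minutes of differential exposure during the first ANT and 25-35 during the PMA-R. The documents do not say how much of the first 10 minutes is spent inside the room. The PMA-R slot spans the cited 30 minutes; the first ANT slot ends 5 minutes before it.

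**3. Air contrast at entry.** The device is "capable of filtering the entire air of a 45 m² room every 10 minutes", which is 6 room volumes per hour, or 3 volumes before minute 0. Assume a well-mixed room of that size that settles at the planned 80% reduction. Other removal is then 1.5 per hour, since 6/(6 + 1.5) = 0.8. The reduction is 0.8 × (1 - e^(-7.5 × 0.5)) = 78% at minute 0 and 0.8 × (1 - e^(-7.5 × 0.667)) = 79% at minute 10. On this assumption students enter at nearly the full contrast.

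**4. Attention sensitivity models.** Let f be the share of the 10 ms effect already present at the first ANT, and r the correlation between the two tests, with equal SDs. The adjusted arm coefficient is 10 - r × (10 f) = 10(1 - r f) ms, with residual SD 90√(1 - r²). Neither r nor f is in the documents. Coefficient, with power at 1,250 per arm in brackets:

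| f | r = 0.3 | r = 0.5 | r = 0.7 |
|---|---|---|---|
| 0 | 10.0 (82.9%) | 10.0 (89.4%) | 10.0 (97.3%) |
| 0.2 | 9.4 (78.1%) | 9.0 (82.3%) | 8.6 (91.7%) |
| 0.5 | 8.5 (69.7%) | 7.5 (67.2%) | 6.5 (71.5%) |
| 1 | 7.0 (53.1%) | 5.0 (36.1%) | 3.0 (21.4%) |

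If effect is proportional to exposure time at mid-test (an assumption), f = 17.5/95 = 0.18. At r = 0.6 the coefficient is 10 × (1 - 0.6 × 0.18) = 8.9 ms.

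**5. Preference models.** Suppose arm shifts a cognitive covariate by the planned 10/90 = 0.11 SD, and its partial correlation with a preference score is 0.1 to 0.3 (assumed). Adjustment then removes 0.11 × 0.1 = 0.01 SD to 0.11 × 0.3 = 0.03 SD. For the post ANT, 0.11 SD is the effect the trial is sized to find. For the PMA-R at 25-35 minutes it is a generous assumption.

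**The case against.** The strongest reply is that little of consequence is touched. The main attention model uses neither test. No SAP rule triggers adjustment for a baseline imbalance. The first ANT ends before the cited 30 minutes, and the cited study concerns brain activity after exposure began (diesel exhaust, by its title), not recovery in filtered air. The illustrated loss for preferences is 0.01-0.03 SD per covariate in a trial sized for 0.11 SD. Giving the PMA-R different roles for different outcomes is a choice, not a contradiction.

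Most of this stands and limits the point. Three stronger readings are tempting, and the documents do not support them:

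- **That the primary attention result is biased.** It is not: the post-ANT contrast adjusts for neither test, so this problem does not reach it.
- **That both tests are certainly early outcomes.** An early effect is possible, more plausibly for the PMA-R than for the first ANT. At f = 0 adjustment is harmless and gains precision. Even at f = 0.2 and r = 0.5, power is 82.3% against 79.3% unadjusted.
- **That adjusted models estimate only the effect arising after minute 25 or 35.** That quantity would be 10(1 - f), whereas the regression gives 10(1 - r f). At r = 0.6 and f = 0.5 these are 5.0 and 7.0 ms, and they agree only at r = 1 or f = 0.

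The reply does not reach the preference regressions. They are planned analyses of primary outcomes and not labelled as sensitivity models. Their control list includes attention outcomes, which are measured 90 minutes or more into exposure.

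**Conclusion.** The point holds in limited form. The timing is certain: neither test precedes differential exposure, and only sex and year of birth are pre-exposure person-level variables. The consequence that matters most is in the five preference models, which as written may condition on part of the effect sought. The size there is probably small (0.01-0.03 SD per covariate) and rests on an assumed shift and assumed correlations. It also rests on reading cognitive ability as the PMA-R and attention outcomes as the post ANT, since the SAP names neither. For attention, only sensitivity models are affected: nothing is lost at f = 0, and about 1.1 of 10 ms is lost at r = 0.6 and f = 0.18. The primary attention contrast stands.

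**What to change.** Amend the SAP only:

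(a) In the main preference models use arm, class strata and the pre-exposure person-level covariates (sex, year of birth). Move the PMA-R and all ANT-derived attention outcomes to named sensitivity models. Removing the PMA-R alone would leave the post-ANT scores in place.

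(b) Label the first ANT and the PMA-R as early in-session measures rather than baseline characteristics, and report their arm contrast.

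(c) State that attention models adjusted for them may be attenuated if filtration acts early. Do not describe them as the effect after minute 25 or 35.

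The cost is a little precision in the main preference models; the adjusted versions remain available as sensitivity analyses.

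Testing the whole class before the split would give true baselines but is not a cheap alternative. Time in the assigned room before the post ANT falls from 90 minutes to 90 - 25 = 65, or to 55 if the 10-minute explanation also comes first. The listed activities already fill 120 minutes, and moving rooms adds more. If effect were proportional to exposure time (assumed), 10 ms would become 10 × 55/90 = 6.1 to 10 × 65/90 = 7.2 ms. Unadjusted power at SE 3.6 ms would then fall from about 79% to about 40-52%.
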